Tianjin Diabetes and Health Cohort Study

Document Date: 2025-05-07

ClinicalTrials.gov ID: NCT06913153

Research Protocol:

This study establishes a multidimensional dynamic cohort research platform leveraging comprehensive medical and healthcare data from approximately 400,000 diabetes patients in Tianjin during 2009-2023. Focused on addressing critical scientific challenges in diabetes prevention and management, the project employs advanced analytical methods to extract insights from multi-parametric data sources including electronic health records, medical imaging, and wearable device metrics.

Diabetes mellitus represents a significant global public health challenge, with its prevalence exhibiting rapid growth in China. Tianjin, serving as the medical hub of the Beijing-Tianjin-Hebei region, possesses a unique advantage through its network of secondary and tertiary hospitals that have systematically accumulated longitudinal medical data. This comprehensive dataset provides an invaluable resource for investigating the spatiotemporal patterns of diabetes epidemiology. In this study, we aim to establish a standardized data integration platform and develop innovative analytical algorithms. Leveraging the Tianjin Diabetes Population Cohort, we will construct an end-to-end research framework encompassing: disease risk prediction models, clinical decision

support systems, and health policy evaluation methodologies.

The research program comprises five synergistic modules designed to provide comprehensive insights into diabetes epidemiology.

The prevalence trends module systematically analyzes the epidemiological characteristics of diabetes and its associated risk factors, while conducting comparative studies with global datasets to establish an evidence-based foundation for researchers worldwide.

In the pathogenesis module, we will investigate the etiological mechanisms, risk factors, early biomarkers, and disease progression of diabetes mellitus and elucidate potential therapeutic targets for diabetes prevention and clinical intervention.

In the risk prediction module, we will develop advanced machine learning ensemble models to identify high-risk populations for diabetes onset, predict the critical diabetic complications including diabetic nephropathy, retinopathy progression, cardiovascular diseases, and assess the life expectancy.

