In the personalized treatment and management module, we will systematically quantify the longitudinal effects of dynamic

glycemic control fluctuations on disease-specific risks and all-cause mortality, investigate medication dosing regimens and prescription patterns in relation to glycemic target achievement, and establish robust clinical evidence to standardize management protocols and optimize tiered care delivery systems for diabetes mellitus.

In the health economics module, we conducted a comprehensive evaluation of diabetes-associated health and economic burdens in Tianjin and developed disease burden trajectories models for temporal trends projection. Furthermore, we performed rigorous health economic evaluations of diabetes interventions through Markov decision-analytic modeling and microsimulation techniques to identify cost-effective diabetes management strategies.

Through the systematic integration of multi-dimensional data, this study will establish a comprehensive closed-loop research framework encompassing risk prediction, clinical intervention, and economic evaluation. This integrated approach will generate region-specific evidence to support precision diabetes prevention and control strategies in the local context.

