Tianjin Diabetes and Health Cohort Study

Document Date: 2025-05-07

ClinicalTrials.gov ID: NCT06913153

Statistical Analysis Plan

Specific processes for analyzing data

1. Define the purpose of the study;
2. Identify the study population;
3. Identify intervention, exposure factors;
4. Identify outcome indicators;
5. Clean and organize data;
6. Study grouping; Missing data handling.

Statistical methods used for each analyzed item:

1. Propensity Score Matching (PSM)
2. Multivariate Parametric Proportional Hazards Model
3. Gompertz Proportional Hazards Model
4. Logistic Regression
5. Cox Proportional Hazards Model
6. Kaplan-Meier Curve
7. Autoregressive Integrated Moving Average (ARIMA) Forecasting Model
8. Bayesian Structural Time Series (BSTS) Model
9. GXboot , Support Vector Machines , Decision Trees , Random Forests
10. Health economics : Cost-Effectiveness Analysis(CAE) , Cost-Utility Analysis(CUA), Cost-Benefit Analysis(CBA)

The way key assumptions are verified:

1. Propensity Score Matching (PSM): PSM required balanced covariates ($SMD < 0.1$) and overlapping propensity score distributions for the exposed and control groups after matching. Balance will be verified by standardized mean difference (SMD), propensity score distribution plots, and between-group tests ($p > 0.05$).
2. Multivariate Parametric Proportional Hazards Model: The model assumes that the risk ratio is constant over time (proportional riskiness) and that the parameter distribution (e.g., Weibull distribution) accurately describes the time dependence. The proportional hazards assumption will first be verified by the Schoenfeld residual test ($p > 0.05$), and the goodness of fit of the model with different parameters will be compared by AIC/BIC.
3. Gompertz Proportional Hazards Model: The model assumes that the risk function follows a Gompertz distribution (exponentially varying) and satisfies proportional riskiness. The distributional assumptions will be verified by plotting the log cumulative hazard linearly versus time and comparing with other parametric models (e.g., Weibull) using the likelihood ratio test.
4. Logistic Regression : Logistic regression requires

continuous variables to be linearly related to the logit, free of multicollinearity and independent of observations. The assumption of linearity will be verified by the Box-Tidwell test, variance inflation factor (VIF<10) will be calculated to exclude multicollinearity, and data will be checked for independent samples.

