
11.Cox Proportional Hazards Model

12.The core assumptions of the Cox model are proportional riskiness and linear association of covariates with log risk. These two assumptions will be tested using the Schoenfeld residual test (global $p>0.05$) and Martingale residual plots, respectively.

13.Kaplan-Meier Curve

14.Kaplan-Meier analyses assumed that censoring was independent of event risk and that the mechanism of censoring was consistent between groups.Randomness of censoring will be indirectly assessed by comparing baseline characteristics of censored and non-censored subjects and by log-rank test results. If censoring is not random, data will be processed using competing risk models or multiple imputation.

15.Autoregressive Integrated Moving Average (ARIMA) Forecasting Model

16. The ARIMA model requires the time series to be smooth and the residuals to be white noise. Stationarity will be verified by the ADF test, and residual autocorrelation will be checked using ACF/PACF plots and the Ljung-Box test ($p>0.05$).

17. Bayesian Structural Time Series (BSTS) Model

18. The BSTS model assumes that the temporal structure (trend, seasonality, etc.) is well set and that the prior distribution matches the data characteristics. The model will be validated by posterior predictive checks, information criteria (WAIC/DIC), and residual normality diagnostics.

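### The ARIMA and BSTS models are checked only on the data used to fit them, so the stated rule can accept a model whose multi-year forecast intervals are too narrow

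*SAP*

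**What the plan says.** The SAP's list of methods names "Autoregressive Integrated Moving Average (ARIMA) Forecasting Model" as item 7 and the BSTS model as item 8. The only text on checking them is in the section on verifying key assumptions.

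- ARIMA (item 16): "Stationarity will be verified by the ADF test", and "residual autocorrelation will be checked using ACF/PACF plots and the Ljung-Box test", with a pass mark of p > 0.05.
- BSTS (item 18): "The BSTS model assumes that the temporal structure (trend, seasonality, etc.) is well set", and then "The model will be validated by posterior predictive checks, information criteria (WAIC/DIC), and residual normality diagnostics".

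The protocol's health economics module says that the team "developed disease burden trajectories models for temporal trends projection". The data come from "approximately 400,000 diabetes patients in Tianjin during 2009-2023".

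Neither document mentions a hold-out period, rolling-origin or temporal cross-validation, a forecast-error measure, interval coverage, a forecast horizon, an interval level or the frequency of the series.

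**The concern.** A forecasting model is judged by how far its forecasts miss and by whether its intervals contain the outcome as often as they claim. The listed checks answer another question: whether the model describes the years already observed. White-noise residuals over 2009-2023 do not show that the slope will hold for the next five years.

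Item 18 names the assumption that matters most for BSTS, the structure of the trend, and then tests it only through fit to past data.

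If these models supply the projections used for policy and economic evaluation, intervals could be published that claim more certainty than they have. The listed checks would give no warning.

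**Working it through.** **1. What each check uses.** ADF uses the observed series. ACF/PACF plots and Ljung-Box use residuals from the fitted series. Posterior predictive checks, WAIC/DIC and residual normality use the fitting data unless some are held out, and no hold-out is described. WAIC estimates predictive accuracy, but from the fitting data and not for multi-year horizons.

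**2. Inputs.** From the documents: 2009-2023 is 15 years, so at most 15 annual or 15 × 12 = 180 monthly points, and a Ljung-Box pass mark of p > 0.05. Assumed, because the documents are silent: nominal 95% intervals, horizons up to 10 years, and a trend whose slope is either fixed or follows a random walk. The plan has no figure of its own to reproduce.

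**3. Analytic check.** Take yearly innovations of SD 1 and a slope that changes by SD q each year. The forecaster knows the current slope, treats it as fixed, and has an interval that is exact one year ahead.

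- True error variance at horizon h: V = h + q² × h(h+1)(2h+1)/6.
- Variance the model assumes: W = h(1 + q²).
- Coverage = 2Φ(1.96 × √(W/V)) − 1.

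| q | h | V | W | Coverage |
|---|---|---|---|---|
| any | 1 | 1 + q² | 1 + q² | 95% |
| 0.1 | 5 | 5 + 0.01 × 55 = 5.55 | 5.05 | 94% |
| 0.1 | 10 | 10 + 0.01 × 385 = 13.85 | 10.1 | 91% |
| 0.3 | 5 | 5 + 0.09 × 55 = 9.95 | 5.45 | 85% |
| 0.3 | 10 | 10 + 0.09 × 385 = 44.65 | 10.9 | 67% |
| 0.5 | 5 | 5 + 0.25 × 55 = 18.75 | 6.25 | 74% |
| 0.5 | 10 | 10 + 0.25 × 385 = 106.25 | 12.5 | 50% |

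The one-year interval is right by construction, so one-step residuals look well scaled while coverage falls with horizon.

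**4. ARIMA by simulation.** Several set-ups were run, with different drift sizes, noise and order-selection rules. The share of fits passing Ljung-Box ranged from 70% to 99%. Five-year coverage of nominal 95% intervals among passing fits was:

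| Series | Drifting slope | Fixed slope |
|---|---|---|
| 15 annual points | 58% to 83% | 81% to 89% |
| 180 monthly points | 38% to 47% | 89% to 92% |

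For a series that is stationary around a linear trend, annual 5-year coverage was 95%.

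One reason for the high pass rate on annual data is low power. With 14 residuals, Ljung-Box detects AR(1) correlation of 0.3, 0.5 or 0.7 with probability 9%, 17% or 29%. With 179 residuals the figures are 74%, 99.8% and 100%.

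**5. BSTS by simulation.** The truth had innovation SD 1 and a slope drifting by SD 0.3 per year (annual series) or 0.05 per month (monthly series). Coverage among fits that passed a Shapiro normality test (p > 0.05) was:

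| Model fitted | Annual, 1/5/10 years | Monthly, 12/60/120 months |
|---|---|---|
| Fixed slope | 94% / 76% / 59% | 83% / 52% / 36% |
| Local linear trend | 96% / 95% / 96% | 99% / 97% / 97% |

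Posterior predictive checks and WAIC/DIC were not simulated.

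**6. Does the remedy detect the problem?** A single hold-out of the last 3 of 15 years does not. It flagged 27% of ARIMA fits under drift (SD 0.3) and 26% with a fixed slope.

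Rolling-origin coverage does move with the problem on average. As drift rose from 0 to 0.30 per year, mean rolling-origin coverage fell from 77% to 63% (annual) and from 91% to 64% (monthly), while true 5-year coverage fell from 82% to 58% and from 92% to 40%. In another set-up it fell from 87% to 81% (annual) and from 91% to 75% (monthly), while true 5-year coverage fell from 89% to 70% and from 90% to 47%. It therefore understates the shortfall.

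**The case against.** **The section is about assumptions.** Its heading concerns verification of assumptions, and the ARIMA checks do that job. Only BSTS is said to be validated. This stands as a point of wording, but no other section evaluates forecasts.

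**The shortfall comes from the assumed truth.** This largely stands. With a fixed slope, annual coverage is already only 81% to 89%, so part of the annual shortfall is not drift; it looks like small-sample model selection. Around a stable trend there was no 5-year shortfall. The simulations show what the rule can let through, not what these data will do.

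**BSTS is not shown to fail.** A reader might infer that BSTS intervals in general will be too narrow. That is not supported: a local linear trend kept coverage at about 95% to 100%, and the SAP does not say which trend will be used. Nor has it been shown that a failing BSTS would pass all of item 18, since two of its three kinds of check were not simulated.

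**The documents do not set the models against each other.** A reader might infer that WAIC/DIC is meant to choose between ARIMA and BSTS, or that both produce the burden projections. Neither is stated. Only ARIMA is labelled as forecasting, and no output is assigned to either model.

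**Rolling origin is weak on annual data.** Cut-offs from 2016 that end in 2023 give three overlapping 5-year forecasts (from 2016, 2017 and 2018), fitted to 8 to 10 points. Coverage can then only be 0, 33, 67 or 100%. In small runs of 100 series per scenario, a score of 3 out of 3 hardly separated good from bad models: later coverage was 82%, 73% and 78% (slope SD 0, 0.15, 0.30), against 76%, 74% and 75% for lower scores. This stands for any single annual series, and it is why the remedy should not rest on annual coverage alone.

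**Conclusion.** The point holds in a limited form. The checks in items 16 and 18 are all made on the fitting data, and they can accept a model whose multi-year intervals are too narrow. Under assumed slope drift, passing ARIMA fits covered roughly 58% to 83% (annual) or 38% to 47% (monthly) at 5 years instead of 95%. Fixed-slope BSTS that passed residual normality also under-covered.

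These sizes rest on the assumed drift, series frequency, horizon and interval level, and they are not estimates for this cohort. A reader might conclude that the shortfall arises whatever the frequency of the series. The simulations do not show that: both frequencies were run under the same adverse drift, and with a fixed slope the monthly shortfall was small. The link from these models to the burden projections is a reasonable inference and not a stated fact.

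The sponsor should make the change, because it is cheap and tests what the models are for.

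**What to change.** Add to items 16 and 18:

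- A rolling-origin evaluation on the 2009-2023 data, using monthly or quarterly series where available. State the series, frequency and horizons. Report forecast error against a naive drift forecast, and the empirical coverage of the forecast intervals at each horizon.
- A sensitivity analysis to trend specification, comparing a fixed slope with a local linear trend. This matters because rolling-origin coverage understates the shortfall.
- Where ARIMA and BSTS project the same series, a comparison based on these results and not on WAIC/DIC, which need a posterior that a likelihood-fitted ARIMA does not have.
- A label of untested on any projection beyond the horizons evaluated.

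Intervals should not be rescaled mechanically from a few overlapping annual forecasts.

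The cost is SAP wording and a few extra fits on existing data. Published intervals may become wider or horizons shorter.
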